12.10 Risks for Males of Childbearing Potential

Recent results from a nonclinical rat fertility study indicated adverse effects on sperm morphology and motility without interference with reproduction were seen at 5.4 times, but not at 2.5 times, the exposure of rezafungin in this study. The risks for rezafungin effects on spermatogenesis in non-human primates and in humans have yet to be defined. Partner pregnancies of male subjects should be followed according to [Section 12.9](#), when possible.

13.0 STATISTICAL METHODS

A Statistical Analysis Plan (SAP) will be prepared and finalized prior to database lock. Any changes to the SAP after it has been signed and prior to the final database lock will be documented in an addendum to the SAP. Any deviations from the final SAP/addendum will be described and justified in the clinical study report. All statistical analyses will be performed using SAS®.

Descriptive statistics, including the numbers and percentages for categorical variables, and the numbers, means, standard deviations, medians, minimums, and maximums for continuous variables, will be provided. Listings of individual subject data will also be produced.

13.1 Analysis Populations

The analysis populations are defined for this study as follows:

- The intent-to-treat (ITT) population will include all randomized subjects, regardless of whether the subject receives study drug.
- The Safety population will include all subjects who received any amount of study drug.
- The mITT population will include all subjects who had documented *Candida* infection based on Central Laboratory evaluation of a culture from blood or another normally sterile site obtained ≤ 4 days (96 hours) before randomization and received ≥ 1 dose of study drug.
- The clinically evaluable (CE) population will include all subjects in the mITT population who also met inclusion criterion #4, did not meet exclusion criteria #1, #2, or #5, had an assessment of both mycological and clinical response at Day 14 in the window of Day 14 (± 1 day) (subjects with invasive candidiasis documented by radiologic/imaging evidence also must have an assessment of radiologic response), and did not have any other factor that could confound the assessment of the global response at Day 14.
- PK Analysis Population will include all Rezafungin for Injection subjects with at least 1 plasma sample obtained for PK analysis.

13.2 Subject Characteristics

Demographics (including age, race, and sex), diagnosis at randomization (candidemia and/or invasive candidiasis), diagnosis methodology (blood culture/rapid IVD and culture specimen obtained from a normally sterile site), ANC at randomization (< 500 cells/ μ L and ≥ 500 cells/ μ L), medical history including subjects diagnosed with COVID-19, *Candida* risk factors, baseline assessments (including height, weight, body mass index [BMI], modified APACHE II score, and Glasgow coma score), mycological data, and systemic signs and symptoms will be summarized in the ITT and mITT populations.

13.3 Study Drug Exposure

Descriptive statistics for the duration of study drug therapy (IV and oral, and separately for IV therapy and oral therapy) will be summarized by treatment group for the mITT and Safety populations. The number and percentage of subjects with 1–7, 8–14, 15–28, and >28 days of exposure will be presented for IV and IV and oral therapy combined. The number and percentage of subjects with 1–3, 4–7, 8–14, 15–28, and >28 days of exposure will be presented for oral therapy. The number and percentage of subjects switching to oral study drug therapy and a frequency distribution of the day of oral switch will be summarized by treatment group for the Safety and mITT populations.

13.4 Efficacy Analyses

For efficacy analyses, subject data will be analyzed in the treatment group to which the subject was randomized.

13.4.1 Primary Efficacy Analyses for the FDA

The primary efficacy outcome for the FDA is ACM at Day 30 (-2 days). The addendum to ICH E9 introduces the concept of an estimand which translates the trial objective into a precise definition of the treatment effect that is to be estimated. The description of the estimand includes four attributes: the population, the variable (or endpoint) to be obtained for each patient, the specification of how to account for intercurrent events (ICE), and the population-level summary for the variable. The estimand attributes for ACM at Day 30 are provided in detail in the SAP.

The number and percentage of subjects in each treatment group who are alive and deceased (or with missing data) at Day 30 will be determined in the mITT population.

The null and alternative hypotheses are the following:

$$H_0: P_1 - P_2 \geq \Delta$$

$$H_1: P_1 - P_2 < \Delta$$

Where:

P_1 = the primary efficacy outcome in the Rezafungin for Injection group,

P_2 = the primary efficacy outcome in the caspofungin group,

Δ = the non-inferiority (NI) margin of 20%.

The NI hypothesis test is a 1-sided hypothesis test performed at the 2.5% level of significance. This is based on the upper limit of the 2-sided 95% CI for the observed difference in the rate of ACM at Day 30 (Rezafungin for Injection group minus the caspofungin group). The primary analysis is based on a CI computed using the unadjusted methodology of Miettinen and Nurminen. If the upper limit of the 95% CI for the difference in rates of ACM at Day 30 in

the mITT population is <20%, the null hypothesis will be rejected and the NI of Rezafungin for Injection to caspofungin will be concluded.

An adjusted 95% CI (adjusted for the randomization stratification factors) will also be computed using the methodology of Miettinen and Nurminen. Cochran-Mantel-Haenszel weights will be used for the stratum weights in the calculation of the CI.

13.4.1.1 Additional Analyses of the FDA Primary Efficacy Outcome

To control the overall alpha level, superiority of rezafungin for ACM at Day 30 will be tested in the following order:

- If NI is declared for ACM at Day 30 in the mITT population and the rate of ACM at Day 30 in the rezafungin treatment group is lower than the caspofungin treatment group, the difference between the treatment groups will be tested for superiority. If the upper bound of the 95% CI is less than 0, superiority of rezafungin will be concluded.
- For the subgroup of subjects with invasive candidiasis, a two-sided 95% CI for the observed difference in the rate of ACM at Day 30 will be calculated using the unadjusted methodology of Miettinen and Nurminen. If superiority is declared in the mITT population for ACM at Day 30 and the rate of ACM at Day 30 in the rezafungin treatment group is lower than the caspofungin group for invasive candidiasis subjects, superiority of rezafungin will be tested. If the upper bound of the 95% CI is less than 0, superiority of rezafungin will be concluded.

All-cause mortality at Day 30 will be assessed separately across the randomization stratification factors of diagnosis (candidemia only; invasive candidiasis) and APACHE II score/ANC (APACHE II score ≥ 20 OR ANC < 500 cells/ μ L; APACHE II score < 20 AND ANC ≥ 500 cells/ μ L). For each subgroup, the number and percentage of subjects alive and deceased at Day 30 will be determined by treatment group in the mITT population. A 2-sided 95% CI for the observed difference in rates of ACM at Day 30 will be calculated in the mITT population using the unadjusted methodology of Miettinen and Nurminen. Other subgroup analyses, including analyses by the pre-, peri-, and post-COVID-19 period will be conducted for descriptive purposes. Depending on the number of subjects in the study diagnosed with COVID-19, ACM at Day 30 may be analyzed in patients with and without COVID-19.

A sensitivity analysis of the primary outcome using multiple imputation methods for missing data, as detailed in the SAP, for subjects whose survival status is not known at Day 30 will be conducted.

13.4.2 Primary Efficacy Analyses for the EMA

The primary efficacy outcome for the EMA is global cure at Day 14 (± 1 day) based on the DRCs determination. Global response is a composite estimand and ICEs are incorporated into the

variable/endpoint. The estimand attributes for global response are provided in more detail in the SAP.

The number and percentage of subjects in each treatment group who have a global response of cure, failure and indeterminate at Day 14 (± 1 day) will be determined in the mITT population.

The null and alternative hypotheses are the following:

$$H_0: P_1 - P_2 \leq -\Delta$$

$$H_1: P_1 - P_2 > -\Delta$$

Where:

P_1 = the primary efficacy outcome in the Rezafungin for Injection group,

P_2 = the primary efficacy outcome in the caspofungin group,

Δ = the NI margin of 20%.

The NI hypothesis test is a 1-sided hypothesis test performed at the 2.5% level of significance. This is based on the lower limit of the adjusted (for the randomization stratification factors) 2-sided 95% CI for the observed difference in global success rate (Rezafungin for Injection group minus the caspofungin group). The primary analysis is based on a CI computed using the method with stratification by Miettinen and Nurminen. Cochran-Mantel-Haenszel weights will be used for the stratum weights in the calculation of the CI. If the lower limit of the 95% CI for the difference in global success rates in the mITT population is $> -20\%$, the null hypothesis will be rejected and the NI of Rezafungin for Injection to caspofungin will be concluded.

To control the overall alpha level, superiority of rezafungin for global response will be tested in the following order:

- If NI is declared and the percentage of subjects that have a global response of cure at Day 14 (± 1 day) as confirmed by the DRC in the rezafungin treatment group is higher than the caspofungin treatment group, the difference between the treatment groups will be tested for superiority. If the lower bound of the 95% CI is greater than 0, superiority of rezafungin will be concluded.
- For the subgroup of subjects with invasive candidiasis, a two-sided 95% CI for the observed difference in global cure at Day 14 for the mITT population will be calculated using the unadjusted methodology of Miettinen and Nurminen. If superiority is declared for the EMA primary efficacy outcome of global response at Day 14 in the mITT population, and the global cure rate in the rezafungin treatment group is higher than the caspofungin group for invasive candidiasis subjects, superiority of rezafungin will be

tested. If the lower bound of the 95% CI is greater than 0, superiority of rezafungin will be concluded.

Global response will also be assessed separately across the randomization stratification factors of diagnosis (candidemia only; invasive candidiasis) and APACHE II score/ANC (APACHE II score ≥ 20 OR ANC < 500 cells/ μL ; APACHE II score < 20 AND ANC ≥ 500 cells/ μL). For each subgroup, the number and percentage of subjects with a global response of cure, failure, and indeterminate at Day 14 (± 1 day) will be determined by treatment group in the mITT population. A 2-sided 95% CI for the observed difference in global cure rates will be calculated in the mITT population using the unadjusted methodology of Miettinen and Nurminen. Other subgroup analyses, including analyses by the pre-, peri- and post-COVID-19 period, will be conducted for descriptive purposes. Depending on the number of subjects in the study diagnosed with COVID-19, global response may be analyzed in patients with and without COVID-19.

The reasons for having a global response of failure or indeterminate at Day 14 (± 1 day) will be presented using the number and percentage of subjects displayed by treatment group in the mITT population. Subjects who miss the efficacy assessment due to COVID-19 will have an indeterminate response and the number and percentage of subjects with an indeterminate response due to COVID-19 will be summarized.

An unadjusted 95% CI will also be computed using the methodology of Miettinen and Nurminen. Additional analyses of the primary efficacy outcome for the EMA, including analyses in the ITT and CE populations, will be described in the SAP.

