2.6. Population Definitions

The following analysis populations will be evaluated and used for presentation and analysis of the data:

- The intent-to-treat (ITT) population will include all randomized subjects.
- The safety population will include all subjects who received any amount of the study drug. Safety assessments will be performed on the safety population. Subjects who receive the wrong study drug for their entire course of study drug will be analyzed in the treatment group based on the drug received. Subjects who receive the wrong study drug for part of their course of study drug will be analyzed in the treatment group based on majority of (i.e., most frequent) doses received.
- The mITT population will include all subjects who had a documented *Candida* infection based on Central Laboratory evaluation of a blood culture or a culture from a normally

sterile site obtained ≤ 4 days (96 hours) before randomization and received ≥ 1 dose of study drug.

- The clinically evaluable (CE) population will include all subjects in the mITT population who also met inclusion criterion #4, did not meet exclusion criteria #1, #2, and #5, had a response other than indeterminate for both mycological and clinical response as assessed by DRC at Day 14 in the protocol specified window of Day 14 \pm 1 day (subjects with invasive candidiasis documented by radiologic/imaging evidence also must have a radiological response by DRC other than indeterminate), and did not receive a concomitant antifungal that could confound the assessment of the global response at Day 14.
- The Pharmacokinetic (PK) population will include all subjects who received any amount of study drug and have at least one blood sample with measurable concentrations.

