4.3. Analysis of Efficacy

Unless otherwise stated, all efficacy analyses will be conducted in the mITT population. Subjects will be analyzed in the treatment group to which they were randomized.

By subject listings of the primary and secondary efficacy outcomes will be provided.

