4.3.1.1. Additional Analyses of the Primary Efficacy Outcomes

Sensitivity analyses of the primary outcome for FDA include:

- The first sensitivity analysis will exclude subjects whose survival status is not known (these subjects are considered deaths in the primary analysis).
- The second sensitivity analysis will calculate an adjusted (for the randomization stratification factors) 95% CI interval using the stratified methodology of Miettinen and Nurminen. As noted above, Cochran Mantel Haenszel weights will be used for the stratum weights in the calculation of the CI.
- The third sensitivity analysis will be conducted using multiple imputation for missing data. Missing primary outcome data will be imputed with multiple imputation. Fifty data sets will be created by treatment group using a logistic regression in which the randomization stratification factors of diagnosis (candidemia only; invasive candidiasis)

and APACHE II score/ ANC (APACHE II score ≥ 20 OR ANC < 500 cells/ μ L; APACHE II score < 20 AND ANC ≥ 500 cells/ μ L) at Screening are included as predictive variables. The seed number of 101305 will be used. The difference in mortality rate is calculated per each imputed dataset and the risk differences are combined using proc mianalyze.

Sensitivity analyses of the primary outcome for EMA include:

- The first sensitivity analysis will consider indeterminate responses as successes.
- The second sensitivity analysis will present an unadjusted two-sided 95% CI for the observed difference in primary outcome rates (Rezafungin for Injection treatment group minus caspofungin treatment group) using the methodology of Miettinen and Nurminen.
- The third sensitivity analysis will analyze the primary outcome for the EMA in the CE population. The number and percentage of subjects with a global response of cure and failure will be provided along with an adjusted (for the randomization stratification factors) two-sided 95% CI for the difference in global cure rates.

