6. CHANGES TO PLANNED ANALYSES

There are no changes between the protocol-defined statistical analyses and those presented in this SAP.

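### The SAP leaves out the ITT analysis of global cure that the protocol names, yet its section 6 reports no changes from the protocol

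*Protocol*

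**What the plan says.** Protocol 13.4.2 makes mITT the primary population for global cure at Day 14 and then promises more work on that outcome, "including analyses in the ITT and CE populations, will be described in the SAP". The details are left to the SAP, but the two populations are named.

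SAP 2.6 defines the first of them: "The intent-to-treat (ITT) population will include all randomized subjects". SAP 4.3 sets the default for efficacy: "Unless otherwise stated, all efficacy analyses will be conducted in the mITT population". SAP 4.3.1.1 then lists three sensitivity analyses for the EMA outcome:

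- The first counts indeterminates as cures instead of failures.
- The next drops the stratification: "The second sensitivity analysis will present an unadjusted two-sided 95% CI for the observed difference in primary outcome rates", by the Miettinen-Nurminen method.
- The last changes the population: "The third sensitivity analysis will analyze the primary outcome for the EMA in the CE population".

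SAP 6 reads in full: "There are no changes between the protocol-defined statistical analyses and those presented in this SAP".

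**The concern.** One protocol sentence names two populations. The SAP carries one of them forward and is silent on the other. A programming team that follows the SAP would drop an analysis the protocol announced, and a reader who relies on SAP 6 would not know it had gone.

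ITT matters here because of how mITT is built. It requires *Candida* confirmed by the Central Laboratory from a sample taken in the 96 hours before randomisation, and at least one dose of study drug. The central result and the fact of dosing are both established after randomisation. CE is a further subset of mITT. Every between-group comparison of global cure in the SAP is therefore made in mITT or in something narrower, and none shows whether the result holds when all randomised subjects are kept.

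**Working it through.** **1. Is an ITT comparison of global cure specified anywhere in the SAP?**

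- SAP 4.3.1 (primary): mITT.
- SAP 4.3.1.1 (EMA sensitivity analyses): the first two state no population, so the mITT default applies. The third is CE.
- SAP 4.3.2 (secondary) and 4.3.3 (subgroups, including timing of culture): mITT.
- SAP 4.3.4: ITT is used, but for Kaplan-Meier survival time and not for global cure.
- SAP 4.1: ITT is used for disposition, deviations, baseline characteristics and culture summaries.
- SAP 4.6: global response is summarised by plasma-concentration tertile in the PK population. SAP 2.6 does not restrict that population to mITT, but only rezafungin samples are assayed, so there is no comparison between groups.
- SAP Appendix 9 (version history): no entry records the removal of an ITT analysis of global cure.

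No such comparison is specified. SAP section 4.3 is present in full, so this is not a gap in the text as extracted.

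**2. Do the plan's own numbers reproduce?** Inputs from Protocol 13.8: cure 70% in both groups, margin 20 points, one-sided alpha 0.025, power 80%, continuity correction, 85% evaluable.

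- Uncorrected: n = 2 × 0.7 × 0.3 × (1.960 + 0.842)² / 0.20² = 82.4 per group.
- Corrected: (n/4) × [1 + √(1 + 4/(n × 0.20))]² = 92.1 per group, against 92 stated.
- Power at 92 per group = Φ[(0.20 − 1/92)/SE − 1.960], with SE = √(2p(1 − p)/92). For p = 0.7 this is 79.9% (80% stated). For mortality, p = 0.2, it is 89.4% (89.7% stated).
- Randomised: 184/0.85 = 216.5, so 217, against about 218 stated.

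The design figures reproduce closely and are not in dispute.

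**3. How many subjects are involved?** 218 − 184 = 34, and 34/218 = 15.6%. This is a planning figure. Protocol 6.2 stops enrolment once 184 subjects qualify for mITT if evaluability is above 85%, which would make the number smaller.

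**4. What would the ITT analysis do to the comparison?** The documents give no cure rate for subjects outside mITT, so these are illustrations under stated assumptions.

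- *Dilution.* Suppose the 34 split evenly, 17 per arm, and all count as not cured. A difference of −20 points in mITT becomes −20 × 184/218 = −16.9 points in ITT, which is inside the margin.
- *Power.* With 109 per group and equal cure rates in the two arms, the overall rate is (92 × 0.70 + 17 × c)/109, where c is the cure rate among the excluded. At c = 0 the rate is 59.1% and the continuity-corrected power 81.7%. At c = 0.70 the rate is 70.0% and the power 86.7%.

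**The case against.** The strongest reply is that the analysis is supportive and may mislead. The EMA hypothesis tests, their alpha and the sample size all rest on mITT, so nothing confirmatory depends on ITT. Counting unassessable subjects as failures in both arms dilutes a true deficit, and in a non-inferiority trial that helps the test drug. This stands. It limits how the ITT result may be read, but it neither removes the protocol's commitment nor makes SAP 6 correct.

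A second reply is practical. The mycological response definitions start from a positive baseline blood or sterile-site culture. Local data may replace missing central data, so some subjects outside mITT can be classified, but someone enrolled on a rapid diagnostic test alone may not fit. The documents also do not say that the DRC adjudicates subjects outside mITT; its procedures are in a charter that is not part of them. This too stands, and it is the reason to fix the rule in advance.

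A third reply is that SAP 1.1.1 allows supportive analyses to be added once data are available. That permission does not pre-specify this analysis.

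In the other direction, a reader might infer that the 34 subjects would appear in no global-cure analysis at all. The documents do not support that: dosed rezafungin subjects outside mITT who have a measurable concentration can enter the tertile summary in SAP 4.6. Nor do they support the inference that the SAP has no ITT efficacy analysis, since survival is analysed there.

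**Conclusion.** The point holds as a discrepancy between protocol and SAP on a supportive analysis. The protocol names ITT and CE for global cure; the SAP specifies only CE; and the no-changes statement in SAP 6 is wrong. The consequence is that about 34 of 218 randomised subjects (15.6%) would be in no between-group comparison of global cure. That size rests on the planned 85% evaluability and falls if evaluability is higher.

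It would go too far to conclude that the EMA primary result is undermined, or that the analysis was dropped on purpose. The primary test does not use ITT, and the documents give no reason for the omission.

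**What to change.** Add to SAP 4.3.1.1 a supportive analysis of Day 14 DRC global cure in ITT. State in advance how subjects with no assessable DRC response are counted (for example, as not cured), and use the same stratified Miettinen-Nurminen interval as in mITT. The protocol prescribes neither the counting rule nor the interval; matching the primary method simply keeps the two results comparable. Correct SAP 6 at the same time.

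If the sponsor decides against the analysis, the alternative is to record and justify its removal in SAP 6. Under SAP 1.1.1, either change is a SAP amendment before database lock and a matter for the clinical study report afterwards.

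The cost is one table and one corrected sentence, plus a check on whether the DRC has responses for subjects outside mITT. The statistical downside is that, under a not-cured rule, cure rates fall in both arms and the difference shrinks toward zero. The text should therefore say that the ITT result is read beside mITT and is not independent proof of non-inferiority.
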